5.2 Derivations and Definitions

- For the preliminary analysis, only PRNT₅₀ will be analyzed included time points Visit 1 (day 0), Visit 3 (day 28) and Visit 5 (day 56). For the final analysis all immunogenicity parameters will be analyzed at all available time points except passive transfer.
- Analysis of passive transfer results are not described in this SAP.
- The primary analysis compares the PRNT₅₀ titer 28 days after last MV-CHIK vaccination between treatment groups. Therefore, titers from Day 56 in Groups A-D will be considered and the titer at Day 28 for Group E.
- Seroconversion rate for anti-Chikungunya PRNT₅₀ titers is defined as proportion of subjects achieving anti-Chikungunya PRNT₅₀ titers ≥ 10 at a certain time point.
- Seroconversion rate for Chikungunya-ELISA is defined as proportion of subjects achieving Chikungunya-ELISA titers ≥ 16 at a certain time point.
- The lower limit of quantification (LLOQ) are not known for immunogenicity parameters at SAP development and therefore the following general rules will apply:
 - In data listings, the original reported value “<LLOQ” will be displayed.

Adapted from:

STAT03_A Statistical Analysis Plan

Version 6.0, Effective Date 16-Feb-2018

Confidential and intellectual property of Assign DMB. No part of this document or its contents may be duplicated, referenced, published or otherwise disclosed in any form or by any means without prior written consent of Assign DMB.

Page 15 of 29

06CJDX

- For calculations the half of the true LLOQ value will be used for such values.

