7.3 Exclusion Criteria

The subject may not be enrolled in the study if any of the following applies:

1. Participation in another clinical study (including exposure to an investigational medicinal product or device) within one month before the screening visit or planned concurrent participation in another clinical study before completion of the treatment period (day 56)
2. History of immunodeficiency, known human immunodeficiency virus (HIV) infection or current hepatitis B/C infection
3. History of drug addiction including alcohol dependence within the last 2 years
4. Inability or unwillingness to avoid intake of more than around 20g alcohol per day during 48 hours after each vaccination (equals roughly 0.5 L beer or 0.25 L of wine)
5. Vaccination within 4 weeks prior to first vaccination or planning to receive any non-study vaccine until end of treatment period (day 56)
6. Prior receipt of any Chikungunya vaccine
7. History of moderate or severe arthritis or arthralgia within the past 3 months prior to Screening Visit
8. Recent infection within 1 week prior to Screening Visit (possibility of deferral)

9. Blood donations including plasma donations, 90 days prior to Screening Visit and anticipated blood, plasma, tissue, sperm or organ donation, throughout the study until end of treatment period (day 56)
10. Clinically relevant history of renal, hepatic, gastrointestinal, cardiovascular, respiratory, skin, haematological, endocrine, inflammatory, autoimmune or neurological diseases or clinically relevant abnormal laboratory values, that in the opinion of the investigator may interfere with the aim of the study
11. History of neoplastic disease (excluding non-melanoma skin cancer that was successfully treated) within the past 5 years or a history of any haematological malignancy
12. Behavioural, cognitive, or psychiatric condition that in the opinion of the investigator affects the ability of the participant to understand and cooperate with the study protocol
13. History of severe adverse reactions to vaccine administration, including anaphylaxis and related symptoms, such as urticaria, respiratory difficulty, angioedema and abdominal pain to vaccines, or history of allergic reaction likely to be exacerbated by any component of the vaccine
14. History of anaphylaxis to drugs or other allergic reactions, which the investigator considers compromising the safety of the volunteer

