8.5 Treatment Period

8.5.1 Visit 1 (day 0)

Subjects found to be eligible will return to site for Visit 1 within 28 days after the screening visit. Inclusion and exclusion criteria will be checked again and (in case of changes since the screening visit) the medical history will be updated. Symptom-directed physical examination, system-based assessment (only if necessary according to findings in symptom-directed physical exam) and vital signs (systolic and diastolic blood pressure, pulse and body temperature) will be recorded. In addition, the subjects will be asked regarding changes in

concomitant medications since the last visit. A serum pregnancy test will be performed in all women.

Blood samples for baseline immunogenicity assessments (measles and Chikungunya antibody ELISA, PRNT₅₀) and isolation of serum for passive transfer will be drawn from an appropriate forearm or cubital vein. For T-cell assays blood samples will be collected and peripheral blood mononuclear cells (PBMCs) will be prepared. For details on laboratory sampling and testing, see section 8.11.

Subjects will be randomised to treatment group A, B, C, D or E and receive their first MV-CHIK vaccination.

The subjects' diaries will be explained and handed over. Subjects will be asked to report their body temperature and any adverse event in these diaries for 7 days, starting 6 hours after the injection.

After observation of the subjects for two hours, local reactions and adverse events (if any occurred) will be recorded.

Blood pressure and pulse rate will be checked, and participants will be discharged only if the investigating physician considers it to be safe for them to leave the department.

The subjects are invited to return to study site for Visit 2 on study day 14 (\pm 1 day).

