8.11.1 Samples for Safety Laboratory Parameters

Safety laboratory parameters will be analysed by local laboratories according to applicable laboratory SOP

The following parameters will be measured to evaluate inclusion and exclusion criteria only once at screening visit (SV).

- Virology: Hepatitis B surface-Ag, anti-Hepatitis B core-Ab, anti-Hepatitis C-Ab, HIV Ab. HIV tests that were performed up to 30 days before screening and where results are available are acceptable and do not require a new test.

The following laboratory parameters will be assessed for subject's safety at screening, Visit 3, Visit 5 and additionally at Early Termination (if applicable) as depicted in Table 2.

- Haematology: haemoglobin, haematocrit, erythrocyte count, differential and total white blood count, platelets
- Chemistry: creatinine, potassium, sodium, calcium, AST, ALT, alkaline phosphatase, bilirubin
- Coagulation parameter: prothrombin time (PT), activated partial thromboplastin time (aPTT), fibrinogen
- Urinalysis: a standard urine test dipstick for determining pH-value, glucose, protein, bilirubin, urobilinogen, blood, leucocytes esterase, nitrite, ketone and specific gravity will be used. In case of abnormal findings, a microscopy will be done for confirmation.
- Laboratory values deviating from the normal ranges defined by the local laboratory will be evaluated by the investigator. Clinically relevant deviations have to be reported as adverse events and graded according to the FDA Guidance for Industry (Toxicity Grading Scale for Healthy Adult and Adolescent Volunteers Enrolled in Preventive Vaccine Clinical Trials, Sept. 2007)

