12.2 Methods of Statistical Immunogenicity Analysis

The immunogenicity analysis will compare the anti-Chikungunya PRNT₅₀ antibody geometric mean titre (GMT) 28 days after the last MV-CHIK vaccination in the Per Protocol (PP) analysis population between the treatment groups. GMTs and GMT ratios will be estimated by applying an analysis of variance including the factor treatment group. This will be done using log₁₀ transformed data and taking the anti-log of the resulting point estimates for the least squares means, least squares means differences and the corresponding 2-sided 95% CIs.

P-values will also be provided to compare GMTs between the treatment groups adjusted for multiple comparisons according to Tukey-Kramer. Likewise, seroconversion rates will be compared between groups.

Seroconversion will be defined as anti-Chikungunya PRNT₅₀ titres ≥ 10 .

Measles- and Chikungunya- ELISA titres will be analysed as described above.

In addition, the long-term stability of anti-Chikungunya antibodies determined by PRNT₅₀ and ELISA, 6 months and one year after the first immunisation, will be analysed compared between the five treatment groups.

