1.2.3.1-1.2.3.6	n/a	Repeat tables 2.1.1-x2.1.6 for PP population (if not the same as Safety Population)	
Immunogenicity Results			
Primary Endpoint			
1.3.1.1	2.3.1.1	GMT of anti-Chikungunya PRNT ₅₀ Antibody 28 days after last MV-CHIK vaccination (mITT Population)	
1.3.1.2	2.3.1.2	ANOVA with fixed factor treatment group for GMT of anti-Chikungunya PRNT ₅₀ Antibody 28 days after last MV-CHIK vaccination (mITT Population)	
Anti-Chikungunya PRNT₅₀ Antibody			
1.3.1.3	2.3.1.3	GMT of anti-Chikungunya PRNT ₅₀ Antibody by Visit (mITT Population)	
 • Preliminary Analysis: Visit 1, 3 and 5 • Final Analysis : All available time points
1.3.1.4	2.3.1.4	ANOVA for GMT of anti-Chikungunya PRNT ₅₀ Antibody between treatment groups by Visit (mITT Population)	
 • Preliminary Analysis: Visit 1, 3 and 5 • Final Analysis : All available time points
1.3.1.5	2.3.1.5	Seroconversion rate for Anti-Chikungunya PRNT ₅₀ Antibody by Visit (mITT Population)	
 • Preliminary Analysis: Visit 1, 3 and 5 • Final Analysis : All available time points
Chikungunya-ELISA Antibodies			
1.3.1.6	2.3.1.6	GMT of Chikungunya-ELISA Antibodies 28 days after last MV-CHIK vaccination (mITT Population)	
1.3.1.7	2.3.1.7	ANOVA for GMT of Chikungunya-ELISA Antibodies between treatment groups 28 days after last MV-CHIK vaccination (mITT Population)	
n/a	2.3.1.8	GMT of Chikungunya-ELISA Antibodies by Visit (mITT Population)	
 • All available time points
n/a	2.3.1.9	ANOVA for GMT of Chikungunya-ELISA Antibodies between treatment groups by Visit (mITT Population)	
 • All available time points
n/a	2.3.1.10	Seroconversion rate of Chikungunya-ELISA Antibodies by Visit (mITT Population)	
 • All available time points
Measles-ELISA antibodies			
n/a	2.3.1.11	GMT of Measles-ELISA Antibodies 28 days after last MV-CHIK vaccination (mITT Population)	
 • All available time points

Adapted from:

Page 21 of 29

STAT03_A Statistical Analysis Plan

Version 6.0, Effective Date 16-Feb-2018

Confidential and intellectual property of Assign DMB. No part of this document or its contents may be duplicated, referenced, published or otherwise disclosed in any form or by any means without prior written consent of Assign DMB.

06CJDX

1.3.1.1 - 1.3.1.7	1.3.2.1 - 1.3.2.11	Repeat tables for PP Population	

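### Seroconversion is defined without a day-0 condition, so it measures seropositivity, and no table gives it at the primary time point

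*Combined protocol and SAP*

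**What the plan says.** Protocol 12.2 states: "Seroconversion will be defined as anti-Chikungunya PRNT₅₀ titres ≥ 10". SAP 5.2 repeats the cut-off as a rate that "is defined as proportion of subjects achieving anti-Chikungunya PRNT₅₀ titers ≥ 10 at a certain time point", and the ELISA rate "is defined as proportion of subjects achieving Chikungunya-ELISA titers ≥ 16 at a certain time point". None of the three refers to the day-0 result or to a fold rise.

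The only chikungunya-specific exclusion in protocol 7.3 is "Prior receipt of any Chikungunya vaccine" (criterion 6). The screening serology in protocol 8.11.1 is "Virology: Hepatitis B surface-Ag, anti-Hepatitis B core-Ab, anti-Hepatitis C-Ab, HIV Ab", with no chikungunya test. Day-0 blood for PRNT50 and ELISA is drawn at Visit 1 (protocol 8.5.1).

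In SAP 7.1, the PRNT50 seroconversion table (1.3.1.5) carries the content note "Preliminary Analysis: Visit 1, 3 and 5", and Visit 1 is the pre-vaccination visit. SAP 2.6 compares seroconversion rates between groups with a Fisher-Freeman-Halton test.

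The primary comparison is of PRNT50 GMTs 28 days after the last MV-CHIK dose: day 56 for Groups A to D and day 28 for Group E (SAP 5.2).

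**The concern.** Conversion means a change from negative to positive. The rule as written looks at one visit only, so antibody that was there before vaccination is counted as a response. That a seroconversion rate is tabulated at Visit 1, when nobody can have converted, shows that the quantity is seropositivity.

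Nothing else in the plan removes such a subject. Past infection is allowed at entry. The per-protocol rules (protocol 12.5.3, SAP 2.9) turn on protocol deviations, and an eligible subject with a positive day-0 titre has committed none. The GMT model has treatment group as its only factor. Fold increase (GMFI) is named in SAP 2.5 but is not a data point in SAP 5.1 and has no table in SAP 7.1.

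Past exposure cannot be ruled out on the protocol's own account. Section 4.2 reports local transmission in Italy and France, imported cases in several European countries, and infection without symptoms. Section 4.4.2 describes a sister trial (MV-CHIK-204) that analyses previously exposed and unexposed subjects separately.

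A second gap is independent of this. Protocol 12.2 says that seroconversion rates are compared in the same manner as the GMTs, but the SAP has no seroconversion table at the primary time point.

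**Working it through.** The plan gives no figure to reproduce: there was no sample size calculation, and no seroprevalence is stated. Group size is 12, with 5 × 12 = 60 in total (protocol 6.3).

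**Effect of one day-0 positive subject in a group.** Suppose the subject stays at or above the cut-off and k of the other 11 respond.

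- Rate under the present rule: (k+1)/12.
- Rate among subjects seronegative on day 0: k/11.
- Overstatement: (k+1)/12 − k/11 = [11(k+1) − 12k]/132 = (11−k)/132.

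| k of 11 | Present rule | Day-0 negatives only | Overstatement (points) |
|---|---|---|---|
| 0 | 1/12 = 8.3% | 0/11 = 0% | 8.3 |
| 6 | 7/12 = 58.3% | 6/11 = 54.5% | 3.8 |
| 10 | 11/12 = 91.7% | 10/11 = 90.9% | 0.8 |
| 11 | 12/12 = 100% | 11/11 = 100% | 0 |

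Keeping all 12 in the denominator would give a difference of 1/12 = 8.3 points at every k. But that scores as a failure someone who had no opportunity to convert, so it is not the fair comparison.

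**How likely is such a subject?** Seroprevalence q is an assumption, shown over a range. The chance of at least one positive is 1 − (1−q)^n. The expected overstatement of a group's rate, with true response s among naive subjects, is [q + (1−q)s] − s = q(1−s). Protocol 4.5 reports earlier rates of up to 96%; s = 50% is an assumed lower case.

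| Assumed q | At least one in 60 | At least one in a given 12 | Expected bias, s = 50% (points) | Expected bias, s = 96% (points) |
|---|---|---|---|---|
| 0.5% | 26% | 5.8% | 0.25 | 0.02 |
| 1% | 45% | 11.4% | 0.5 | 0.04 |
| 2% | 70% | 21.5% | 1.0 | 0.08 |
| 5% | 95% | 46.0% | 2.5 | 0.2 |

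**Effect on a GMT.** If the day-0 positive subject's titre is m times the level of the other 11, the group GMT is multiplied by m^(1/12). For m = 10 this is 1.21, and for m = 50 it is 1.39. The values of m are assumptions; the documents give none. For scale, with an assumed log10 SD of 0.4 to 0.6 and 55 residual degrees of freedom (t = 2.004), the unadjusted 95% CI half-width for a GMT ratio is 2.004 × SD × √(2/12). That is 0.327 to 0.491 on the log10 scale, or a factor of about 2.1 to 3.1 either way.

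**Primary time point.** SAP 7.1 gives GMT tables at 28 days after the last MV-CHIK dose for PRNT50 (1.3.1.1, 1.3.1.2) and chikungunya ELISA (1.3.1.6, 1.3.1.7). Seroconversion appears only by visit (1.3.1.5, 2.3.1.10). A test at Visit 3 compares all groups after one dose. A test at Visit 5 compares Groups A to D 28 days after their second dose with Group E 56 days after its only MV-CHIK dose. Neither is the contrast used for the GMTs.

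**The case against.** The best defence is that this is mostly a loose label. The trial has one site, in Belfast, and few volunteers there are likely to have had chikungunya. Randomisation makes any imbalance a matter of chance. The Visit 1 row shows day-0 positives by group, and the SAP 7.2 listings show them by subject. If that row reads 0 of 12 in every group, the present and the proposed definitions give identical results. Seroconversion is a supporting comparison, and in a naive population a baseline covariate in the ANOVA would be almost constant. Rates for A to D at day 56 and for E at day 28 can both be read from table 1.3.1.5.

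Most of this stands, and it limits the size of the point. A reader might infer that the trial's responder rates and GMTs are inflated, or that the rates cannot be read as vaccine-induced at all. The documents do not support either: both need a seropositive subject to enrol, and the Visit 1 row would reveal one.

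What does not stand is that visibility is enough. Showing a day-0 positive does not take that subject out of later rates or out of the Fisher-Freeman-Halton test. SAP 2.4 unblinds the sponsor personnel and statisticians who perform and review the day-56 analysis, so a handling rule chosen after that would be post hoc. Being able to read two rates from different rows of a by-visit table is also not a planned comparison.

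**Conclusion.** The point holds as a definition that should be corrected, with a small expected effect. The rule measures seropositivity, and nothing in eligibility, screening or the per-protocol criteria stops a day-0 positive from counting as a responder. One such subject overstates a group's rate by (11−k)/132. Taking 8.3 points as the typical size would be wrong, since it requires that no naive subject in the group responds; near the earlier rates of up to 96% the shift is below 1 point. The average effect over the assumed range of seroprevalence is 0.02 to 2.5 points.

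A reader might also infer that the primary GMT comparison is compromised and that day-0 positives must leave the per-protocol population. That goes too far. The factor of 1.21 to 1.39 rests on an assumed titre multiple and is small beside the assumed width of a GMT ratio interval. Protocol 12.5.3 also ties per-protocol exclusion to deviations, which these subjects do not have. A sensitivity analysis is the proportionate answer.

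The missing seroconversion table at the primary time point holds whether or not anyone is seropositive on day 0.

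**What to change.** - In the protocol (synopsis and 12.2) and SAP 5.2, define seroconversion as day-0 PRNT50 <10 and post-vaccination ≥10, among subjects seronegative on day 0. For ELISA, use day-0 <16 and post-vaccination ≥16.
- Report the present quantity under the name seropositivity, including its Visit 1 row, and list day-0 positives by group.
- Keep the primary per-protocol GMT population as protocol 12.5.3 defines it, and add a GMT sensitivity analysis without day-0 positives.
- Add a seroconversion table at 28 days after the last MV-CHIK vaccination (day 56 for Groups A to D, day 28 for Group E), with exact 95% CIs and the planned Fisher-Freeman-Halton test.
- Settle all of this before the unblinding for the day-56 analysis.

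The cost is a wording change in both documents, one table and one sensitivity analysis. The SAP alone is not enough, because the cut-off stands in the protocol and SAP 2.13 says that analyses follow it. No new sample is needed. The downside is that any day-0 positive reduces a denominator of 12.

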6. SAFETY ANALYSIS

All safety analyses will be performed for the safety population.

6.1 Extent of Exposure

6.1.1 Data Points

The following information will be analyzed descriptively in tables and corresponding details on the subject level will be provided in data listings:

- Treatment duration
- Study duration
- Study vaccine administration (will be listed only)

6.1.2 Derivations and Definitions

- Treatment duration [days] = date of last administered vaccine – date of first vaccination +1
- Study duration [days] = date of last attended visit (or date of study discontinuation, if applicable) – date of signed informed consent + 1

6.2 Adverse Events

6.2.1 Data Points

The following analyses will be provided for all Adverse Events:

- Adverse event overview for solicited and unsolicited events (e.g. any AE, any SAE, any related AE). This table will include a statistical test for comparison of treatment groups (see [Section 2.6](#)).
- Solicited Adverse Events by symptom
- Solicited Adverse Events by symptom and severity
- Unsolicited Adverse Events by SOC and PT, overall and for specific types of Adverse Events (e.g. SAEs, related AEs)
- Unsolicited Adverse Events by severity and for specific types of Adverse Events
- Unsolicited Adverse Events by causality and for specific types of Adverse Events

Specifications of TLFs are provided in [Section 7](#).

6.2.2 Derivations and Definitions

- All solicited and unsolicited Adverse Events up to day 56 (Visit 5) will be analyzed for the preliminary analysis. AE reporting and documentation is completed at Day 56. Thus all AE in the database are considered for the adverse event endpoints. In case of unexpected data change, new reported AEs or follow-up information, affected tables and/or listings may be repeated for the final analysis. Otherwise,

Adapted from:

STAT03_A Statistical Analysis Plan

Version 6.0, Effective Date 16-Feb-2018

Confidential and intellectual property of Assign DMB. No part of this document or its contents may be duplicated, referenced, published or otherwise disclosed in any form or by any means without prior written consent of Assign DMB.

Page 16 of 29

06CJDX

adverse event tables are not repeated at the final analysis. This decision may be done in a DRM prior to database closure, see [Section 2.9](#).

- Percentages for AE rates are based on N (treatment group totals).
- Medical Conditions/symptoms noted prior to first IMP administration will be reported as medical history and not as adverse events. In case of an incomplete start date where it cannot clearly be decided if the Adverse Event started before the first IMP the Adverse Event will be considered to be started before first IMP.
- An Adverse Events is considered to be related to study treatment if “Relationship to Study Treatment” is answered with “definitely”, “probably” or “possibly” or the causality is missing.
- Adverse Events where an action was taken are considered if “Action taken with Study Treatment” is answered with “Second IMP Administration Delayed” or “Second IMP not Administered”.
- Tables showing “severe” events will include events with grade 3 or 4 or missing grade.
- In tables showing subjects with AEs by maximum severity, subjects will be counted only in the highest grading category, but events will be counted in each reported grading category.
- In tables showing AEs by causality, subjects will be counted only in the strongest relationship category, but events will be counted in each category.

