8.2 Randomisation

At Visit 1 (day 0) 60 eligible subjects will be randomly assigned to one of five treatment groups (A, B, C, D or E) by means of randomisation envelopes provided by data management.

Each subject will be assigned a unique three-digit randomisation number, stated on the envelope in ascending order. Only trained members of the unblinded study team will be authorised to open one envelope per subject, containing the information about the allocated treatment group.

Upon opening, the randomisation envelope shall be signed with date and time of randomisation and the number of the randomised subject shall be written down on it.

All 60 subjects will be equally distributed between the 5 groups using a randomisation ratio of 1 : 1 : 1 : 1 : 1 = A : B : C : D : E

A subject will be considered enrolled once the first IMP administration has been performed according to randomisation.

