12.3 Methods of Statistical Safety Analysis

The analysis of safety will be performed by means of descriptive measures in the Safety Population. Solicited and unsolicited AEs (local and systemic) will be analysed descriptively.

AEs and concomitant diseases will be coded using the MedDRA coding dictionary.

Solicited AEs (reactogenicity):

Solicited local and systemic AEs gathered by the subjects' diaries will be summarised for the 7-day period, by AE grading (mild, moderate, severe) and by treatment group. The number and percentage of subjects with AEs will be presented. Fisher exact tests will be provided for a comparison of AE rates between treatment groups in summary tables.

Unsolicited AEs:

Separately, the number and percentage of subjects with unsolicited/spontaneous adverse events (AEs), medically-attended AEs (MAEs) and serious adverse events (SAEs) will be presented for each treatment group overall, and by system organ class/preferred term, by AE grade, and relatedness. Fisher exact tests will be provided for a comparison of AE rates between treatment groups.

Laboratory values and vital signs as well as changes in laboratory values from baseline will be analysed descriptively by time point and treatment group.

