12.7 Missing Data

All attempts will be made to prevent missing data and generally, missing will not be imputed, and analysis will be limited to observed values. However, for missing data in AE evaluation (e.g. missing information about severity or causality) a worst-case approach will be applied.

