2.5 Descriptive Analyses

Descriptive analyses of continuous variables (summary statistics) will be described with the number of non-missing observations, arithmetic mean, standard deviation (\pm SD), median, quartiles (Q1 and Q3) and range (minimum and maximum).

Descriptive analysis of continuous immunogenicity variables (i.e. tables for the GMT and GMFI) will be described with the number of non-missing observations, geometric mean, confidence intervals for the geometric mean, standard deviation of logarithmic values, median, quartiles (Q1 and Q3) and range (minimum and maximum).

Categorical variables (frequency statistics) will be described with the number of non-missing observations and percentages (%). Percentages will be calculated within each stratum on the total number of non-missing observations, if not stated otherwise.

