2.8 Handling Missing Data

Generally, missing values of immunogenicity variables will not be imputed, and the analysis will be limited to observed values. For missing data in AE evaluation concerning seriousness, severity or causality a worst case approach will be applied. In case of missing assignment to solicited or unsolicited, this AE will neither be counted in tables for solicited AEs nor in tables for unsolicited AEs but in tables for all AEs.

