2.11 Analysis Populations

2.11.1 Safety Population

The safety population is defined to include all subjects who entered into the study and received at least one IMP administration. All analysis based on the safety population will be carried out using the actual treatment received. Subjects with vaccination protocol deviations will be allocated to a treatment group after a case-by-case review in the Blind Data Review Meeting. If a subject received different doses at different visits, the minimum dose received will decide the treatment group.

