			
 • Any related severe solicited systemic AEs • Any solicited systemic SAEs • Any related solicited systemic SAEs • Any medically attended solicited systemic AEs • Any related medically attended solicited systemic AEs • Any solicited systemic AEs leading to study discontinuation • Any solicited systemic AEs leading to second vaccination not administered
1.4.6	n/a	Summary Table of unsolicited Adverse Events (Safety Population)	
 • Any unsolicited AEs • Any related unsolicited AEs • Any severe unsolicited AEs • Any serious unsolicited AEs • Any medically attended unsolicited AEs • Any related severe unsolicited AEs • Any related serious unsolicited AEs • Any related medically attended unsolicited AEs • Any unsolicited AEs leading to second vaccination not administered • Any unsolicited AEs caused study discontinuation
1.4.7	n/a	Subjects with at least one Adverse Event classified by Maximum Severity (Safety Population)	
Solicited Adverse Events			
1.4.8	n/a	Subjects with solicited local Adverse Events by Symptom (Safety Population)	
1.4.9	n/a	Subjects with solicited systemic Adverse Events by Symptom (Safety Population)	
1.4.10	n/a	Subjects with solicited Adverse Events classified by Maximum Severity (Safety Population)	
1.4.11	n/a	Subjects with solicited local Adverse Events by Symptom classified by Maximum Severity (Safety Population)	
1.4.12	n/a	Subjects with solicited systemic Adverse Events by Symptom classified by Maximum Severity (Safety Population)	
Unsolicited Adverse Events			
1.4.13	n/a	Subjects with unsolicited Adverse Events by SOC and PT (Safety Population)	
1.4.14	n/a	Subjects with related unsolicited	

Adapted from:

Page 23 of 29

STAT03_A Statistical Analysis Plan

Version 6.0, Effective Date 16-Feb-2018

Confidential and intellectual property of Assign DMB. No part of this document or its contents may be duplicated, referenced, published or otherwise disclosed in any form or by any means without prior written consent of Assign DMB.

06CJDX

		Adverse Events by SOC and PT (Safety Population)	
1.4.15	n/a	Subjects with severe unsolicited Adverse Events by SOC and PT (Safety Population)	
1.4.16	n/a	Subjects with serious unsolicited Adverse Events by SOC and PT (Safety Population)	
1.4.17	n/a	Subjects with medically attended unsolicited Adverse Events by SOC and PT (Safety Population)	

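### SAP 6.2.2 divides solicited adverse-event counts by the full group size, so a subject with no diary data and no reaction found at a visit is counted as reaction-free

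*Combined protocol and SAP*

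**What the plan says.** SAP 6.2.2 (Adverse Events, derivations) states: "Percentages for AE rates are based on N (treatment group totals". It makes no distinction between solicited and unsolicited events. The group totals are those of the safety population, defined in SAP 2.11.1: "The safety population is defined to include all subjects who entered into the study and received at least one IMP administration". Having diary data is not a condition of entry.

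This is an exception to the SAP's general rule in 2.5: "Percentages will be calculated within each stratum on the total number of non-missing observations, if not stated otherwise".

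Protocol 12.3 describes the source of solicited events: "Solicited local and systemic AEs gathered by the subjects' diaries will be summarised for the 7-day period". Protocol 12.7 gives the general principle on missing data: "missing will not be imputed, and analysis will be limited to observed values". For adverse events, SAP 2.8 adds: "For missing data in AE evaluation concerning seriousness, severity or causality a worst case approach will be applied". It also covers an event not assigned as solicited or unsolicited. Neither document has a rule for a diary that is blank or not returned.

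The solicited tables in SAP 7.1 (1.4.3 to 1.4.5 and 1.4.8 to 1.4.12) count subjects, for example "Subjects with solicited local Adverse Events by Symptom (Safety Population". No listed table or listing gives the number of subjects who supplied diary data.

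**The concern.** A full-group denominator suits events that are reported spontaneously, because silence there reasonably means no event. Solicited reactions are different: they are measured by asking each subject to record listed symptoms every day. If the record does not exist, the outcome is unknown. The SAP nevertheless enters it as no reaction, unless a visit happened to find one.

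The error runs in the reassuring direction. The rate of solicited events is a secondary endpoint, and the groups are compared on it with Fisher's exact test (protocol 12.3, SAP 2.6). If diary loss differed between groups, part of any difference in reported rates would reflect record-keeping rather than reactogenicity. A reader of the tables could not see this, because the number of subjects with diary data is not shown. For laboratory data, by contrast, SAP 6.3.1 does plan to report how many subjects had samples drawn.

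**Working it through.** The documents state no expected reaction rate, diary-loss rate or power for this trial, so there is no figure of the plan's own to reproduce. The check is denominator arithmetic.

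**Inputs**
- Group size: protocol 8.2 says "All 60 subjects will be equally distributed between the 5 groups", so 60/5 = 12 per group. Protocol 8.9.2 does not replace subjects after randomisation.
- Illustrative true rates p, from the phase I results in protocol 4.4.1: 50.0% (injection-site pain) and 23.8% (related fatigue). Both symptoms are solicited here too. They set the scale and are not predictions.
- m = subjects in a group with no diary data and no reaction found at a visit. This is assumed to be 1 or 2; the documents give no value.

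**Direction.** Let x subjects have a recorded reaction, and let y of the m unobserved subjects (0 ≤ y ≤ m) have reacted. The SAP reports x/12. Complete data would give (x + y)/12, which is never smaller. The reported rate is therefore correct or too low, and never too high for this reason.

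**Expected size.** If missingness is unrelated to reaction, the expected reported rate is p × (12 − m)/12. Each such subject removes 1/12 = 8.3% of the true rate in relative terms.

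| True rate p | m = 0 | m = 1 | m = 2 |
|---|---|---|---|
| 50.0% | 50.0% | 0.50 × 11/12 = 45.8% | 0.50 × 10/12 = 41.7% |
| 23.8% | 23.8% | 0.238 × 11/12 = 21.8% | 0.238 × 10/12 = 19.8% |

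Two groups that both have a true rate of 50%, one with m = 0 and one with m = 2, would be expected to report 50.0% and 41.7%. That is a gap of 8.3 points with no difference in reactogenicity.

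**Effect on a given table entry.** Changing the denominator to 12 − m gives:

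| Reactors x | x/12 (SAP) | x/11 (m = 1) | x/10 (m = 2) |
|---|---|---|---|
| 3 | 25.0% | 27.3% | 30.0% |
| 6 | 50.0% | 54.5% | 60.0% |

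With m = 0 nothing changes.

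**The case against.** **The diary is not the only source.** Protocol 11.6 has the investigator inspect the injection site two hours after each injection and at later visits, and these findings are entered as adverse events. Protocol 10.2 and 11.5 have events asked about and recorded at each visit to day 56. Withdrawn subjects are to attend an early termination visit (protocol 8.9), at which Table 2 schedules diary collection. This stands, and it makes the route to having no data narrow. It does not close it. The two-hour inspection comes before the first diary entry at six hours. Visit 2 falls on days 13 to 15, after the 7-day window has ended, and the sample questions in 10.2 are general. The SAP also does not say how a reaction found only at a visit is to be classed.

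**The SAP may set an exception.** SAP 2.5 applies unless another rule is stated, and 6.2.2 states one, so the SAP does not contradict itself. SAP 2.8 also words the observed-values rule for immunogenicity variables only. Both points are fair. The conflict is with the general principle in protocol 12.7.

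**Two stronger readings should be set aside.** A reader might infer that a subject who misses the second injection is also counted as reaction-free. The documents do not support this. The listed tables count each subject over the whole period to day 56 and are not split by vaccination, so a reaction to the first injection still counts. A subject who did not react to the only injection received is a true non-event for that exposure. A reader might also infer a breach of the worst-case rule. That rule concerns missing attributes of an event already recorded, such as severity or causality, and does not reach an absent diary.

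**Conclusion.** The point holds as a minor one. SAP 6.2.2 treats a subject with no diary data and no reaction found at a visit as free of solicited reactions, so the solicited rate can only be understated. The expected relative loss is 8.3% per such subject in a group of 12: at a true 50%, that is 4.2 points for one subject and 8.3 points for two.

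These sizes rest on two assumptions: a value for m that the documents do not supply, and diary loss unrelated to reaction. The effect disappears if all diaries are returned, and shrinks to the extent that visits recover reactions. The documents give no reason to expect heavy or unequal diary loss, so nothing here shows that the group comparison will in fact be distorted. The case for change is that the correction is cheap and would make any loss visible.

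**What to change.** In SAP 6.2.2, keep the treatment-group total as denominator for unsolicited and serious adverse events. For solicited tables 1.4.3 to 1.4.5 and 1.4.8 to 1.4.12:

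- use as denominator the subjects with at least one post-injection diary entry, whatever it shows, and draw the numerator from the same subjects;
- show that count in each column header;
- keep the all-treated version, including reactions found only at visits, as a sensitivity table.

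Eligibility for the denominator must not depend on the result. Admitting a subject without a diary only when a reaction was seen would push rates up. For example, take 10 subjects with diaries and 5 reactors, plus 2 without diaries, one of whom had a reaction seen at two hours. That rule gives 6/11 = 54.5%, against 5/10 = 50.0% on diary data and 6/12 = 50.0% on the full group.

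The cost is some SAP wording, one flag and an extra set of tables. Diaries are already collected and checked for completeness at Visits 2 and 4. Where diaries are missing, reported rates will usually be slightly higher. A reaction seen only at a visit in a subject without a diary will appear only in the sensitivity table and the listings. Partly completed diaries still count as observed, so days left blank remain a smaller, unaddressed gap.
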